#### 8.1.2 Serious Adverse Event (SAE)

An SAE is defined per 21CFR§312.32 as "any AE occurring at any dose that suggests a significant hazard, contraindication, side effect, or precaution." This includes but is not limited to any of the following events:

- 1. Death.
- 2. A life-threatening event. A life-threatening event is any adverse therapy experience that, in the view of the investigator, places the patient or subject at immediate risk of death from the reaction as it occurred.
- 3. Inpatient hospitalization or prolongation of existing hospitalization. Please note that hospital admissions for the purpose of conducting a protocol-mandated procedure do not need to be reported as an SAE, unless the hospitalization is prolonged due to complications.
- 4. Persistent or significant disability.
- 5. An event that required intervention to prevent permanent impairment or damage. An important medical event that may not result in death, be life threatening, or require hospitalization may be considered an SAE when, based on appropriate medical judgment, it may jeopardize the subject and may require medical or surgical intervention to prevent one of the outcomes listed in this definition.
- 6. Congenital anomaly or birth defect.
- 7. Other conditions specified in the protocol.

Regardless of the relatedness of the AE to study drug, the event must be identified as an SAE if it meets any of the above definitions.

In addition, events that occur at a higher frequency then expected frequency, as determined by appropriate medical judgment, may be considered SAEs.

#### 8.1.3 Unexpected Adverse Event

An AE is considered "unexpected" when its nature (specificity) or severity is not consistent with the protocol or the available product information (i.e. package insert, the investigational plan, or the investigator's brochure), such as safety information provided in the summary of product characteristics

(SPC), for an authorized medicinal product in the European Community, which is being used according to the terms and conditions of the marketing authorization.

## 8.2 Adverse Events 8.2.1 Collecting Procedure

AEs that are associated with a protocol-mandated procedure, that is not part of the normal standard of care, and hypoglycemic events will be collected beginning immediately after the consent document has been obtained. All other AEs will be collected immediately after randomization. All AEs will continue to be collected until study completion, or for 30 days after the subject prematurely withdraws from the study. AEs will be followed until the time the event is resolved, stabilized, or the participant completes or withdraws from the study, whichever occurs first.

AEs may be discovered through any of these methods:

- Observing the subject.
- Questioning the subject, this should be done in an objective manner.
- Receiving an unsolicited complaint from the subject.
- An abnormal value or result from a clinical or laboratory evaluation (e.g., a radiograph, an ultrasound, or an electrocardiogram) can also indicate an AE. If this is the case, then the evaluation that produced the value or result should be repeated until the value or result returns to normal or can be explained and the subject's safety is not at risk. If an abnormal value or result is determined by the investigator to be clinically significant, it must be reported as an AE.

## 8.3 Recording Procedure

Throughout the study the investigator will record all adverse events on the appropriate AE case report form (CRF) regardless of their severity or relation to study medication or study procedure. The investigator will treat all subjects experiencing AEs appropriately and observe them at suitable intervals until their symptoms resolve or their status stabilizes.

#### 8.3.1 Grading and Attribution

#### **GRADING CRITERIA**

The study site will grade the severity of adverse events experienced by CIT study subjects according to the criteria set forth in the current version of the *Terminology Criteria for Adverse Events in Trials of Adult Pancreatic Islet Transplantation.* This document (referred to herein as the *CIT-TCAE* manual) provides a common language to describe levels of severity, to analyze and interpret data, and to articulate the clinical significance of all adverse events.

AE severity will be graded on a scale from 1 to 5 according to the following standards in the *CIT*-*TCAE* manual:

Grade 1 = mild adverse event Grade 2 = moderate adverse event Grade 3 = severe and undesirable adverse event Grade 4= life-threatening or disabling adverse event Grade 5 = death

Grade 2 and higher adverse events will be reported. Grade 1 events do not require reporting.

AEs, not included in the CIT-TCAE listing, should be recorded and graded 1 to 5 according to the General Grade Definition provided below:

Grade 1	Mild	Transient or mild discomforts (< 48 hours), no or minimal medical intervention/therapy required, hospitalization not necessary (non-prescription or single-use prescription therapy may be employed to relieve symptoms, e.g., aspirin for simple headache, acetaminophen for post-surgical pain).
Grade 2	Moderate	Mild to moderate limitation in activity some assistance may be needed; no or minimal
		intervention/therapy required, hospitalization possible.
Grade 3	Severe	Marked limitation in activity, some assistance usually required; medical intervention/therapy
		required, hospitalization possible.
Grade 4	Life-	Extreme limitation in activity, significant assistance required; significant medical/therapy
	threatening	intervention required, hospitalization or hospice care probable.
Grade 5	Death	Death.

#### Table 5. General Grade Definitions

All AEs will be reported and graded, by the PI or designee, whether they are or are not related to disease progression or treatment.

#### **DEFINITION OF ATTRIBUTION**

Attribution will only be determined and collected for serious adverse events.

The relatedness, or attribution, of an adverse event to an investigational product will be determined by the site investigator. The site investigator will also record the determination of attribution on the appropriate CRF and/or SAE report form. The relationship of an AE to the study treatment will be defined by using the descriptors provided below.

Code	Descriptor Definition							
	UNRELATED CATEGORY							
1	1 Unrelated The adverse event is clearly not related to the investigational agent(s).							
		RELATED CATEGORIES						
2	Unlikely	The adverse event is doubtfully related to the investigational agent(s).						
3	Possible	The adverse event may be related to the investigational agent(s).						
4	Probable	The adverse event is likely related to the investigational agent(s).						
5	Definite	The adverse event is clearly related to the investigational agent(s).						

 Table 6. CIT-TCAE attribution of adverse events

For additional information and a printable version of the CIT-TCAE manual, consult the CIT website: http://isletstudy.org.

#### 8.3.2 Outcome Categories and Definitions:

All AEs classified as serious or severe or possibly/probably related to the trial product must be followed until the patient has recovered, stabilized, recovered with sequelae or died, and until all queries related to these adverse events have been resolved.

All other AEs must be followed until the patient has recovered or stabilized or until 30 days after the end of the trial, and until all adverse event related queries for the patient have been resolved.

Furthermore, the sponsor will at examination of the SAE reports evaluate which reports that should be reported to the concerned competent authorities and Ethic Committees according to the criteria's outlined below.

- **Recovered**= Fully recovered or by medical or surgical treatment the condition has returned to the level observed from the first trial related activity after the patient signed the informed consent.
- **Stabilized=** This outcome should only be used for cancer events and chronic conditions that cannot be normalized by medical or surgical treatment. This term should only be used when the patient has completed the protocol.
- **Recovered with Sequelae=** As a result of the AE, the patient suffered persistent and significant disability/incapacity (e.g. became blind, deaf, paralyzed). Any AE recovered with sequelae should be rated as an SAE.
- Not yet recovered
- Fatal
- Unknown

## 8.4 Serious Adverse Events

#### 8.4.1 Collecting Procedure

Serious adverse events (SAEs) will be collected following the subject's written consent to participate in the study until 30 days after the participant completes or withdraws from the study. SAEs will be followed until the time the event is resolved, stabilized, or until 30 days after the subject completes or withdraws from the study, whichever comes first.

#### 8.4.2 Recording Procedure

SAEs will be recorded on the AE CRF and on the SAE form. The DCC will complete the CIOMS form for submission to the European Health Authorities.

#### 8.4.3 Reporting Procedure

The following process for reporting a serious adverse event ensures compliance with the ICH guidelines and 21CFR §312.32.

#### 8.4.3.1 REPORTING CRITERIA FROM SPONSOR TO HEALTH AUTHORITY

After the SAE has been assessed, the event will be reported to the appropriate health authorities in the required manner based on the following criteria:

- **No reporting.** This requirement applies if the AE is deemed not serious by the DCC medical reviewer and the NIAID / NIDDK medical monitor.
- **Standard reporting** (i.e., will be included in the annual report to the health authorities). This requirement applies if the AE is classified as any of the following:
  - 1. Serious, expected, and drug related.
  - 2. Serious, expected, and *not* drug related.
  - 3. Serious, *unexpected*, and not drug related.

• **Expedited reporting.** This requirement applies if the AE is considered serious, unexpected, and drug related. This type of SAE must be reported by the sponsor to the appropriate health authorities within 15 days; fatal or life-threatening events must be reported within 7 days.

#### 8.4.3.2 REPORTING TIMELINE- FROM THE SITE TO THE DCC

When an investigator identifies an SAE (as defined in section 8.1.2), he or she must notify the DCC Safety Reporting Center within 24 hours of discovering the event. The investigator must ensure that these events are entered on the electronic SAE CRF. In the event that the eCRF cannot be submitted (*i.e.* computer failure), the site must fax a paper SAE report to the DCC within 24 hours of discovering the event.

# 8.4.3.3 REPORTING TIMELINE- FROM THE DCC TO THE SPONSOR AND HEALTH AUTHORITIES

The DCC is responsible for notifying the sponsor within 2 business days of receiving the report from the clinical site. The sponsor is responsible for disseminating appropriate reports to the health authorities, and all investigators in the study. SAEs per 21 CFR 312.32 definitions, except elective hospitalizations, will be reported to the Health Authority by the study sponsor (NIAID) in accordance with applicable regulations.

#### 8.4.3.4 NOTIFYING THE DATA AND SAFETY MONITORING BOARD

The NIAID/NIDDK will provide the DSMB with listings of all SAEs on an ongoing basis, at least yearly.

#### 8.4.3.5 NOTIFYING ETHICS COMMITTEE

The investigator will ensure the timely dissemination of SAE information, including expedited reports, to the Ethics Committee (EC) in accordance with applicable regulations and guidelines.

#### 8.4.3.6 REPORTING PREGNANCY AS A SERIOUS ADVERSE EVENT

Any pregnancy that occurs during a clinical study that is using an investigational drug must be reported to DCC utilizing the SAE report form. This report is *for tracking purposes only*. All pregnancies that are identified during the study must be followed to conclusion and the outcome of each must be reported. The investigator should report all pregnancies within 24 hours using the SAE report form. The investigator should counsel the subject and discuss the risks of continuing with the pregnancy and the possible effects on the fetus. A woman who becomes pregnant or wishes to while on the study will be counseled as to her choices and will be encouraged to discuss those choices with her obstetrician. Monitoring of the subject should continue until the conclusion of the pregnancy, and a follow-up SAE report form detailing the outcome of the pregnancy should be submitted.

#### 8.4.4 Updating Source Documentation

Documents describing the safety profile of a drug, such as the investigator's brochure, will be amended as needed by the study drug manufacturer to ensure that the description of safety information adequately reflects any new clinical findings. Until these documents are updated, expedited reporting will be required for additional occurrences of a reaction.

## 8.5 Suspected Unexpected Serious Adverse Reactions (SUSARs)

All suspected adverse reactions related to the investigational medicinal product (IMP, i.e. LMW-DS) that are both unexpected and serious are subject to expedited reporting.

The sponsor shall report all the relevant safety information regarding fatal or life-threatening SUSARs to the concerned competent authorities and Ethic Committees as soon as possible but not later than 7 calendar days after the sponsor has first knowledge of the minimum criteria for expedited reporting. In

each case relevant follow-up information should be sought and a report completed and communicated to the competent authorities and Ethic Committees within an additional eight calendar days.

The sponsor shall inform all investigators concerned of relevant information about SUSARs that could adversely affect the safety of subjects.

## 8.6 Other safety issues requiring expedited reporting

All non fatal and non life-threatening SUSARs must be reported to the competent authority and the Ethics committee in the concerned Member States as soon as possible but no later than 15 calendar days after the sponsor has first knowledge of the minimum criteria for expedited reporting. Further relevant follow-up information should be given as soon as possible. The same time frame shall also be used for expedited reporting of safety issues that might alter the current benefit-risk assessment of the IMP or that would be sufficient for considering changes in the IMP administration or in the overall conduct of the trial, for instance;

- Single case reports of an expected serious adverse reaction with an unexpected outcome (e.g.: a fatal outcome)
- An increase in the rate of occurrence of an expected serious adverse reaction, which is judged to be clinically important
- Post-study SUSARs that occur after the patient has completed a clinical trial and are reported by the investigator to the sponsor

## 9. MECHANISTIC ASSAYS

## 9.1 Metabolic Testing

All subjects will use a study provided One Touch Ultra glucometer or an approved glucometer and/or CGMS unit identified in the MOP for measuring capillary glucose levels. Investigators should instruct subjects to measure and keep notes of pre and postprandial plasma glucose and requirement of insulin. Data should be recorded before breakfast, at lunch and dinner, and then two hours after each of these meals, and once in the evening. If the subject becomes free of insulin it is sufficient to record the data of blood/plasma glucose two days per week up until 12 months post transplant. Subject diaries should be collected as specified in Appendix I, Schedule of Events, and kept as source documentation. Glucometers will be collected and measurements downloaded as specified in the Schedule of Events.

### 9.1.1 Study Endpoints

Designated primary and secondary endpoints will be employed to compare each treatment group ("LMW-DS" and "State of the Art"). Because the assessment of islet graft function is dependent on complex physiologic relationships between the graft and its recipient, a number of different tests will be performed. The stimulated c-peptide for the Mixed Meal Tolerance Test (MMTT) will be used as the primary endpoint, and additional stimulatory tests of islet graft function utilizing glucose (FSIGT) challenges will be performed to assess secondary endpoints. Also, the effect of islet graft function on glycemic control (HbA1c), glycemic lability (MAGE and LI), hypoglycemia (Clarke and HYPO scores), glucose variability (CGMS), and quality of life (QOL) will be assessed as additional secondary endpoints. (See section 4.1 for endpoint description).

#### 9.1.1.1 INSULIN REQUIREMENTS

Subjects will record their total daily insulin dose on self-monitoring diaries. Subject should be given exogenous insulin as needed to maintain fasting capillary glucose levels 5-9 mmol/L and avoiding hypoglycemia.

## 9.1.1.2 GLYCEMIC CONTROL

Glycemic control will be assessed by HbA1c (%), which will be analyzed centrally at the University of Washington.

#### 9.1.1.3 GLYCEMIC LABILITY

Glycemic lability will be assessed by both the mean amplitude of glycemic excursions (MAGE) and the lability index (LI).

The MAGE requires 14 – 16 capillary blood glucose (BG) measurements over two consecutive days taken before and 2-hours after breakfast, lunch, and dinner, and at bedtime with an optional measurement at 3 AM. A glycemic excursion is calculated as the absolute difference in peak and subsequent nadir (or vice versa) glucose values, with the direction (peak to nadir versus nadir to peak) determined by the first quantifiable excursion in the two day period. All excursions > 1 S.D. of the 7 – 8 glucose readings for the day in which they occurred qualify for the analysis, where they are summed and divided by the number of qualified excursions to give the MAGE in mmol/L (or mg/dL) glucose. A MAGE > 11.1 mmol/L (200 mg/dl) is indicative of marked glycemic lability.

The LI requires 4 or more daily capillary BG measurements over a 4 week period and is calculated as the sum of all the squared differences in consecutive glucose readings divided by the hours apart the readings were determined (range 1 to 12 hours) in  $(mmol/L^2/hr \cdot wk^{-1})$ . A LI greater than or equal to the 90th percentile (433 mmol/L/hr ·wk) of values derived from an unselected group of type 1 diabetes (T1D) patients is evidence for severe glycemic lability.

#### 9.1.1.4 HYPOGLYCEMIA

An episode of severe hypoglycemia is defined as an event with one of the following symptoms: memory loss, confusion, uncontrollable behavior, irrational behavior, unusual difficulty in awakening, suspected seizures, loss of consciousness, or visual symptoms in which the subject was unable to treat him/herself and which was associated with either a blood glucose level < 54 mg/dL (3.0 mmol/L) or prompt recovery after oral carbohydrate, IV glucose, or glucagon administration.

In addition, composite indices of hypoglycemia frequency, severity, and symptom recognition will be assessed by the Clarke survey and the HYPO score.

The Clarke survey involves subject completion of eight questions scored by the investigator according to an answer key that gives a total score between 0 and 7 (most severe), where scores of 4 or more indicate reduced awareness of hypoglycemia and increased risk for severe hypoglycemic events.

The HYPO score involves subject recording of BG readings and hypoglycemic events (BG < 3.0 mmol/L [54 mg/dL]) over a 4-week period and recall of all severe hypoglycemic episodes in the previous 12-months. A HYPO score greater than or equal to the 90th percentile (1047) of values derived from an unselected group of T1D patients indicates severe problems with hypoglycemia.

#### 9.1.1.5 MIXED-MEAL TOLERANCE TEST (MMTT)

Basal (fasting) and stimulated glucose and c-peptide levels will be determined using the MMTT. Subjects will be instructed not to eat or inject short-acting (or bolus) insulin after 8 PM the night before the test. Evening or bedtime administration of long-acting insulin will be permitted, as will consumption of water. Subjects receiving CSII (insulin "pump" therapy) may remain on the basal rate of insulin. Subjects will arrive fasting to the transplant or diabetes clinic where the capillary BG will be checked. If the BG is < 70 mg/dL (3.9 mmol/L) or > 136 mg/dL (8.0 mmol/L), the test will be rescheduled for the next possible day. If the BG is 70 – 136 mg/dl (3.9-8.0 mmol/L), basal glucose and c-peptide levels will be drawn. Immediately after, the subject will receive 6 ml per kg body weight (to a maximum of 360 mL) of Boost® High Protein Drink or Resource Protein Drink (or a nutritionally equivalent substitute) to consume in 5 minutes starting at time = 0. Then, at time =15, 30, 60, 90 and 120 minutes, stimulated glucose and c-peptide levels will again be drawn.

Each blood sample for c-peptide and glucose determination will be drawn according to University of Washington (Seattle, WA) standard protocol. Each sample will be shipped frozen to the University of Washington for measurement by the core laboratory.

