#### Figure 4: Study Design Schema: Enrollment, Screening, Randomization, and Transplantation

#### **4.1 Study Endpoints** 4.1.1 Primary Endpoint

The level of stimulated c-peptide at 90-minutes derived from the mixed-meal tolerance test (MMTT) at 75+5 days following the first islet infusion.

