### 4.1.3.1 FULL ISLET GRAFT FUNCTION DEFINITION:

Islet transplant recipients are considered to have full islet graft function if all of the following criteria are met:

- Titrated off insulin therapy for at least 1 week (7 consecutive days) with the last day within the day 75 and day 365 windows;
- HbA1c <7.0% or a 2.5%% decreased from baseline at the end of the 7 day period when titrated off insulin;
- Fasting capillary glucose level should not exceed 140 mg/dL (7.8 mmol/L) more than three times in the past week (based on measuring capillary glucose levels a minimum of 7 times in a seven day period);
- 2-hour post-prandial capillary glucose should not exceed 180 mg/dl (10.0 mmol/L) more than three times in the past week (based on measuring capillary glucose levels a minimum of 21 times in a seven day period);
- Fasting serum glucose level ≤ 126 mg/dL (≤7.0 mmol/L) from central lab results; if the fasting serum glucose level is > 126 mg/dL (>7.0 mmol/L), it must be confirmed in an additional one out of two measurements;
- Evidence of endogenous insulin production defined as fasting or stimulated C-peptide levels ≥ 0.5 ng/mL (≥0.16 nmol/L) at the end of the 7 day period when titrated off insulin.

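### The upper glucose limit for starting the primary-endpoint MMTT is given as 136 mg/dL and 8.0 mmol/L, which are not equal, so the start rule contradicts itself for readings of about 137-144 mg/dL

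*Protocol*

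**What the plan says.** Section 4.1.1 defines the primary endpoint as "The level of stimulated c-peptide at 90-minutes derived from the mixed-meal tolerance test (MMTT"), measured 75 ± 5 days after the first islet infusion. Section 10.2.1 repeats this definition.

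Section 9.1.1.5 describes how the test is run. The subject arrives fasting and capillary glucose is checked. The section then gives the start rule in two sentences:

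- **Reschedule.** The test is put off if the reading is too low ("If the BG is < 70 mg/dL (3.9 mmol/L") or too high ("> 136 mg/dL (8.0 mmol/L), the test will be rescheduled for the next possible day").
- **Proceed.** "If the BG is 70 – 136 mg/dl (3.9-8.0 mmol/L), basal glucose and c-peptide levels will be drawn".

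Each limit is given in both units. The upper pair, 136 mg/dL with 8.0 mmol/L, is the same in both sentences. No other section corrects it, and none says which unit governs.

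**The concern.** The two upper limits are offered as one value in two units, but they do not convert to each other. Between them lies a strip of readings where one limit stops the test and the other lets it go ahead.

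The number is a decision threshold. It determines whether the test behind the primary endpoint is run on the day or put off. The same test also feeds the β-score (section 9.1.1.6) and the C-peptide to glucose, creatinine ratio (section 9.1.1.7), and the latter section recognises that C-peptide output varies with prevailing glucose. A start limit exists to standardise that starting condition, so it needs a single value. As written, staff faced with a reading in the strip cannot tell which action follows the protocol, and a monitor cannot tell whether the action taken was a deviation.

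**Working it through.** **Inputs, all from the protocol**

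- Upper start limit: 136 mg/dL, equated with 8.0 mmol/L (9.1.1.5, twice).
- Lower start limit: 70 mg/dL, equated with 3.9 mmol/L (9.1.1.5).
- Other glucose pairs, used to find the conversion factor the document itself applies: "should not exceed 140 mg/dL (7.8 mmol/L) more than three times in the past week" and "2-hour post-prandial capillary glucose should not exceed 180 mg/dl (10.0 mmol/L") (4.1.3.1), the 126 mg/dL (7.0 mmol/L) fasting serum limit (4.1.3.1), "BG < 3.0 mmol/L [54 mg/dL"] (9.1.1.4), and "A MAGE > 11.1 mmol/L (200 mg/dl) is indicative of marked glycemic lability" (9.1.1.3).

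**Step 1. The factor implied by each pair** (mg/dL divided by mmol/L)

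| mg/dL | mmol/L as stated | Ratio | mg/dL ÷ 18.0 | Agrees to one decimal |
|---|---|---|---|---|
| 54 | 3.0 | 18.00 | 3.00 | yes |
| 70 | 3.9 | 17.95 | 3.89 | yes |
| 126 | 7.0 | 18.00 | 7.00 | yes |
| 140 | 7.8 | 17.95 | 7.78 | yes |
| 180 | 10.0 | 18.00 | 10.00 | yes |
| 200 | 11.1 | 18.02 | 11.11 | yes |
| **136** | **8.0** | **17.00** | **7.56** | **no** |

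The six comparison pairs, including the lower limit of this same rule, give ratios of 17.95 to 18.02. One further pair, 100 mg/dL with 5.5 mmol/L in section 9.1.1.9, is off only in the last digit (100/18.0 = 5.56).

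**Step 2. Try to reproduce the stated equality**

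- 136 / 18.0 = 7.56 mmol/L; with the finer factor, 136 / 18.016 = 7.55 mmol/L.
- 8.0 × 18.0 = 144.0 mg/dL; 8.0 × 18.016 = 144.1 mg/dL.

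The equality does not reproduce with either factor.

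**Step 3. Could rounding explain it?** A value printed as 8.0 stands for 7.95 to 8.05 mmol/L, which is 7.95 × 18.0 = 143.1 to 8.05 × 18.0 = 144.9 mg/dL. The figure of 136 lies well outside that range, so rounding does not explain the gap.

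**Step 4. Width of the gap**

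- 144 − 136 = 8 mg/dL.
- 8.0 − 7.55 = 0.45 mmol/L.

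**Step 5. What the rule says inside the gap**

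| Reading | mg/dL limit | mmol/L limit |
|---|---|---|
| up to 136 mg/dL (from the lower limit) | proceed | proceed |
| about 137-144 mg/dL (7.6-8.0 mmol/L) | reschedule | proceed |
| above 144 mg/dL | reschedule | reschedule |

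**Step 6. Can such readings occur?** Section 9.1.1.1 aims for fasting capillary glucose of 5-9 mmol/L, and 7.6-8.0 lies inside that range. The document therefore expects readings of this size. It gives no distribution of fasting values at day 75, so the share of subjects in the strip cannot be calculated.

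**The case against.** The strongest reply accepts the arithmetic and disputes the consequence.

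- **Units in use.** All seven centres are in Scandinavia (section 4). A study meter is supplied, with alternatives only if approved in the Manual of Procedures (section 9.1). Several glucose limits that staff act on elsewhere are in mmol/L only: the insulin targets in 5.11 and 9.1.1.1, and the FSIGT start limits in 9.1.1.8. If everyone reads mmol/L, one rule applies throughout and the mg/dL figure does nothing.
- **Effect of a reschedule.** A reading in the strip would usually cost a short delay. The visit window is ± 5 days (section 7.7), and section 10.2.1 accepts a later value obtained before any further infusion. The lowest observed value is substituted only when there is no later one.
- **Size of the strip.** Either limit already admits a wide range of starting glucose: 7.55 − 3.9 = 3.65 mmol/L or 8.0 − 3.9 = 4.1 mmol/L. The disputed strip is 0.45 mmol/L.
- **Same text for both arms.** Nothing in the rule favours either treatment.

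All of this stands, and it limits what may be concluded. A reader might infer that sites apply different rules to the same subject. The protocol does not say that any site reads mg/dL while another reads mmol/L. A reader might also infer that tests become non-comparable or that subjects end up imputed; the width of the strip and the provisions above do not support that. The trial is open-label, so a reader might suspect that staff could use the ambiguity to favour one arm, but the document shows no direction for such an effect.

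The reply does not remove the contradiction. Consistent use of mmol/L would leave the error without effect, but the protocol does not name mmol/L as the governing unit.

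**Conclusion.** The point holds in a narrow form. The upper start limit in section 9.1.1.5 is wrong as written: its two figures differ by about 8 mg/dL (0.45 mmol/L), and for readings of about 137-144 mg/dL the rule gives opposite instructions. This rests only on the unit conversion, which the protocol's own other pairs confirm, and not on any assumption about the trial's data.

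The effect on the trial cannot be put in numbers. Any percentage of subjects affected would rest on an assumed distribution of fasting glucose, because a titration target is not a distribution. No effect on power, type I error or the difference between arms is shown. The point matters because the threshold controls the start of the primary-endpoint test and correcting it is cheap.

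**What to change.** In section 9.1.1.5, reconcile the mg/dL and mmol/L figures for the upper limit so that they convert correctly. Make the same change in the reschedule sentence and the proceed sentence, and state which unit governs if a reading falls between rounded values. The sponsor must decide which limit was intended; this review does not choose between them. Any site worksheet or Manual of Procedures text that carries the pair should be brought into line.

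The cost is a corrected figure in two sentences plus a short statement of the governing unit, which can go into the next protocol amendment. Sample size, visit schedule and analysis are unaffected.
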